7.2 CONCOMITANT DISEASES AND MEDICATION

Descriptive statistics are planned for concomitant therapy collected in eCRF. Medications will be coded by World Health Organization Drug Dictionary (WHO-DD) version Sep 2019.

Medication collected in eCRF “Concomitant therapy” will be classified as Prior only if start and stop prior to the date of first dose of study medication, if a medication starts before the date of first dose of study medication and stops on or after the date of first dose of study medication, then the medication will be classified as both Prior and Concomitant. Medications will be classified as Concomitant only if they have a start date on or after the date of first dose of study medication.

If medication start and/or stop dates are missing or partial, the dates will be compared as far as possible with the date of first dose of study medication. Medications will be assumed to be Concomitant only, unless there is clear evidence (through comparison of partial dates) to suggest that the medication started prior to the first dose of study medication. If there is clear evidence to suggest that the medication started prior to the first dose of study medication, the medication will be assumed to be both Prior and Concomitant, unless there is clear evidence to suggest that the medication stopped prior to the first dose of study medication. If there is clear evidence to suggest that the medication stopped prior to the first dose of study medication, the medication will be assumed to be Prior only.

Incomplete dates of medication/therapy will be imputed as detailed below:

Start Date: If start date is completely missing and end date is not prior to first dosing, then the medication will be classified as concomitant. If start date is completely missing and end date is prior to first dosing, then the medication will be classified as prior.

If (year is present and month and day are missing) or (year and day are present and month is missing) then set month and day to January 1. If year and month are present and day is missing then set day to first day of month.

End Date: If end date is completely missing then the medication will be classified as concomitant. If (year is present and month and day are missing) or (year and day are present and month is missing) then set month and day to December 31. If year and month are present and day is missing, then set day to last day of the month.

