7.6 PRIMARY ANALYSES

All patients treated with afatinib will be included in the analysis of the primary outcome, Time on Treatment (TOT) on afatinib.

The TOT with afatinib is defined as time from the start of afatinib to last dose date of afatinib or death date by any cause, which comes first.

Refer to Table 7.6: 1 for the rules for determining TOT with afatinib event or censoring date. The analysis of TOT with afatinib will be performed on Treated Set (TS). Those analyses will be conducted as one of the interim analyses mentioned in [section 7.11](#).

Table 7.6: 1 Rules for determining TOT event or censoring date

Rule #	Situation	Outcome	Date of event or censoring
1	Patients lost to follow up without providing end date of treatment during afatinib treatment period	censor	Date of last known date of contact during afatinib treatment period
2	Patients still receive ongoing first-line afatinib treatment at end of study period	censor	Date of last known date of contact during first line afatinib treatment period

Proprietary confidential information © 2024 Boehringer Ingelheim International GmbH or one or more of its affiliated companies

Rule #	Situation	Outcome	Date of event of censoring
3	Other situations	event	Date of last treatment during first line afatinib treatment period

The last known date of contact will derive as follows:

For subjects who withdrew from study or became lost to follow-up, the date last known of contact will be based on the last assessment date/visit date or the date of the last dose of study drug or end of study date, whichever occurs later.

If last known of contact date is later than cut-off date, use cut-off date as last known of contact date.

Kaplan-Meier estimates and two-sided 90% confidence intervals for the 25th, median, and 75th percentiles of the survival distribution will be calculated, the Brookmeyer-Crowley method^[4] based on log-log transformation will be used to construct the 90% CI, the standard error of the Kaplan-Meier quartile estimates will be estimated using Greenwood's formula. Kaplan-Meier curves will also be produced.

For the purpose of calculating TOT, incomplete first line afatinib treatment end dates will be imputed as below:

If month and year are present and day is missing:

- If year=year of first dosing and
 - If month = month of first dose then set day to day of first dose
 - If month > month of first dose then set day to first day of month

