- If year > year of first dose then set day to first day of month

For all other cases, the missing dates will not be imputed and the subject will censored at last known of contact date and censored situation will be missing treatment end date.

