7.7 SECONDARY ANALYSES

7.7.1 OS from the start of afatinib until the date of death

OS is defined as the time from the start of afatinib until death for any reason. Subjects who have not died at the time of the statistical analysis will be censored at the time they were last known contact.

OS will be analyzed in a similar fashion with primary analysis. Analysis will be provided for population set TS.

The swimlane plot of overall survival by subsequent treatment will be provided.

For the purposes of displaying the subsequent treatment duration in plot, incomplete second line treatment start/end and third line treatment start dates will be imputed as below:

If month and year are present and day is missing for treatment start date:

Proprietary confidential information © 2024 Boehringer Ingelheim International GmbH or one or more of its affiliated companies

- Set day to the first day of month

If month and year are present and day is missing for treatment end date:

- If year=year of treatment start date and
 - If month = month of treatment start date then set day to last day of month
 - If month > month of first dose then set day to first day of month

For all other cases, the missing dates will not be imputed and partial dates will not be displayed on plot.

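### A missing afatinib stop day is imputed to the earliest possible date, so an imputed time on treatment can be too short but never too long; the effect on the median is small.

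*SAP*

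**What the plan says.** SAP 7.6 defines the primary endpoint, TOT, as "time from the start of afatinib to last dose date of afatinib or death date by any cause, which comes first". In Table 7.6: 1, patients who are not censored have an event dated at "Date of last treatment during first line afatinib treatment period". The stop date is therefore the event time.

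The same section then says that "incomplete first line afatinib treatment end dates will be imputed as below". When only the day is missing there are three branches:

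- stop in the month and year of first dose: "If month = month of first dose then set day to day of first dose"
- stop in a later month of the same year: "If month > month of first dose then set day to first day of month"
- stop in a later year: "If year > year of first dose then set day to first day of month"

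Any other incomplete stop date is left unimputed and the patient is censored at last known contact. Section 7.6 gives no reason for choosing the early day and plans no sensitivity analysis around it.

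The SAP handles partial dates in three other places:

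- **7.10.1, adverse event onset.** The first-dose-month line is word for word the one used for the stop date.
- **7.2, end of concomitant therapy.** "If year and month are present and day is missing, then set day to last day of the month".
- **7.7.1, end of second-line treatment, for the swimlane plot.** A stop in the start month follows "If month = month of treatment start date then set day to last day of month". A stop in a later month of the start year is set to day 1, in the same words as 7.6.

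**The concern.** For an adverse event onset, an early date is the cautious choice because it keeps the event treatment-emergent. That reasoning does not carry over to the end of a duration. There, the earliest possible date shortens the quantity being estimated, and it does so in the same direction for every affected patient.

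Protocol 9.1 describes the study as descriptive with no group comparisons. Its product is an estimated median with quartiles and a 90% interval. No test is being protected, so an early date is not conservative in any useful sense. It is simply an error of known sign in the primary endpoint.

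The rule also ignores other dates that the study may hold. Protocol 9.3 collects dates of dose modification, and SAP 6.7 gives a first-line visit window of 28 -7/+2 days. A dose or an on-treatment visit recorded within the stop month could narrow the range of possible stop dates, but 7.6 does not use it when it fills in the day.

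**Working it through.** The documents give no figure for the effect of this rule, so there is none to reproduce. The check has three steps.

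**Inputs.** TOT is exponential with a median of 12 months and N = 76 (Protocol 9.5). First doses run from May 2020 to December 2021 (Protocol 6). The planned 90% CI width is at most 11 months (Protocol 9.9.3). The share of stop dates with a missing day is not given, so it is an assumption, shown from 5% to 100%.

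**Step 1: direction.** Error = imputed stop minus true stop.

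- In the first-dose month the true stop lies on or after the first-dose day, and the imputed stop is that day.
- In a later month the true stop lies on or after day 1, and the imputed stop is day 1.

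The error is therefore zero or negative in every branch. It is exactly zero only when the true stop falls on the imputed day.

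**Step 2: size per imputed patient.** If stop days are spread evenly over a month of average length 30.44 days, the mean error in a later month is about -(30.44 - 1)/2 = -14.7 days. A simulation of 300,000 patients under the inputs above, with the 7.6 rule applied to each, gave:

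- range -30 to 0 days, with exactly zero error in 3.5%
- stops after the first-dose month: mean -14.6 days
- stops within the first-dose month (2.9% of patients): mean -9.8 days
- overall: 0.971 × (-14.56) + 0.029 × (-9.78) = -14.4 days, and 14.4/30.44 = 0.47 month

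For a stop in the first-dose month, the imputed stop equals the first dose. TOT is then 0 days by date difference, or 1 day if the +1 convention for study day in SAP 6.7 is applied. Section 7.6 does not say which.

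**Step 3: effect on the median.** Around the median the exponential density changes little over one month. If a share f of stop dates is imputed, the median moves by roughly f × (-0.47) month. Two simulations agree with this. One took Kaplan-Meier medians over 4,000 studies of 76 patients (19 months' accrual, cut at 43 months). The other took the median of the 300,000 patients, whose true median was 11.99 months.

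| Share of stop dates lacking the day | f × (-0.47) | Kaplan-Meier, N = 76 | Large-sample median (shift) |
|---|---|---|---|
| 5% | -0.02 | – | 11.96 (-0.03) |
| 10% | -0.05 | -0.05 | 11.93 (-0.06) |
| 20% | -0.09 | -0.10 | 11.89 (-0.10) |
| 30% | -0.14 | -0.15 | – |
| 50% | -0.24 | -0.25 | 11.76 (-0.23) |
| 100% | -0.47 | – | 11.50 (-0.49) |

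The large-sample medians are in whole days, so they resolve to about 0.03 month. Against the planned interval width, 0.10/11 = 0.9% and 0.49/11 = 4.5%.

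**Alternatives under the same inputs.** Mid-point imputation has a mean error of -0.5 day, and the median is 11.96 months if every stop date is partial. Last-day imputation has a mean error of +14.7 days and a median of 12.48 months.

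**The case against.** The strongest objection is that the point is immaterial. A shift of 0.05 to 0.10 month is under 1% of the planned interval width, and no decision rule depends on it. Partial stop dates may also be rare. Data are entered prospectively, queries are raised continuously (Protocol 9.6.2), and critical data are fully verified (Protocol 9.8). The documents do not list which data are critical, but the stop date is an obvious candidate. The rule is also prespecified and cannot overstate time on the sponsor's drug. All of this stands as to size. It does not remove a one-directional error that is cheap to avoid.

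Some stronger readings are tempting, and the documents do not support them:

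- **Every imputed TOT is too short.** About 3.5% are exact under the assumptions used. The sound statement is that none can be too long.
- **An early stop gets a TOT of zero.** This depends on a day-count convention that 7.6 does not state.
- **All missing stop dates bias TOT short.** Dates missing more than the day are censored at last known contact, which can fall after the true stop. The net direction over all incomplete dates is not determined.
- **The SAP contradicts its own end-date practice.** Its other rules are mixed. Concomitant therapy and same-month second-line stops take the last day of the month, but later-month second-line stops take day 1, as in 7.6. Those rules serve classification and plotting, so they set no precedent for a duration.
- **The rule will place a stop before documented treatment.** This is possible but not shown. Table 7.6: 1 dates the event at last treatment, so a recorded later dose may already inform it, and a visit after stopping conflicts with nothing.
- **The rule was copied from the adverse event section.** The shared wording suggests this but does not establish it.

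**Conclusion.** The point holds as a minor one. For stop dates missing only the day, SAP 7.6 always chooses the earliest possible date. The imputed primary-endpoint time can therefore never be too long, and it is short by about half a month on average (0 to 30 days).

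On a 12-month median the shift is about -0.05 to -0.10 month if 10% to 20% of stop dates lack the day, and about -0.5 month if all do.

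The direction follows from the rule alone. The size rests on exponential TOT with a 12-month median, stop days spread roughly evenly within months, and an assumed share of partial dates. Neither simulation includes the 30% dropout of Protocol 9.5. Nothing here suggests that the study's conclusions would change unless partial dates are common.

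**What to change.** In SAP 7.6, replace the three day-missing branches with the mid-point of the possible dates. With no further information this is day 15, or midway between first dose and month end when the stop falls in the first-dose month. The imputed date should fall no earlier than the last documented afatinib dose or the last visit with treatment recorded as ongoing. It should fall no later than death or the start of second-line treatment. State the day-count formula for TOT in the same place.

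List the patients with an imputed stop date, and report the median with all such dates set first to the earliest and then to the latest possible day. If 20% of dates were partial, those two runs would give about 11.89 and 12.09 months against a true 11.99.

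The cost is a few lines of SAP text and a little programming, with no new data. The downside is that an individual TOT could then be overstated, which the present rule rules out. In return, the mean error falls from -14.4 days to about -0.5 day.

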9.3 VARIABLES

This is a prospective, observational study. Clinical data will be collected and entered directly into the eCRF during or after the patient visit per study protocol. The study protocol does not mandate treatments, each participating site provides and documents patient care and outcomes according to usual care, physician discretion and local practice standards. Thus, study variables may not be available for all patients at all data collection time points per routine medical care. All the data will be continuously and directly into the eCRF during or after the patient visit in the whole study period.

The study variables to be collected include:

- Date of diagnosis
- Demographics: age at the start of afatinib treatment, gender, smoking status
- Laboratory test: hematology, biochemistry and urine examinations. List below table 2:

Table 3. Laboratory test

Category	Parameters
Hematology	Hemoglobin, platelet count, white blood cell (WBC), absolute neutrophil count (ANC)
Chemistry	Electrolytes: Sodium and potassium Liver function tests: Alkaline phosphatase, aspartate amino transferase (AST/SGOT), alanine amino transferase (ALT/SGPT), γ -glutamyltransferase (GGT), total bilirubin Renal function parameters: Blood urea/Blood Urea Nitrogen (BUN), creatinine Other: Glucose, albumin, phosphorus, lactate dehydrogenase (LDH), total protein,
Urinalysis	pH, protein, glucose, blood/erythrocytes, leucocytes, nitrite; in case of clinically significant finding further evaluation should be performed and results documented. Dipstick testing is sufficient.

- Stage of disease at the start of afatinib treatment
- Tumour histology

- Type of EGFR mutations at the start of afatinib and subsequent treatment, specifically the type of acquired resistance mutation
- Sites of metastases at start of afatinib treatment
- Body weight and height at the start of afatinib treatment
- Eastern cooperative oncology group (ECOG) performance score (PS) (if available) at start of afatinib treatment
- Date of start and end of afatinib treatment
- Starting dose of afatinib
- Afatinib dose modification(s) and date(s) (if applicable)
- ECOG PS (if available) at start of subsequent treatment
- Sites of metastases at the start of subsequent treatment
- Reason for discontinuation of afatinib treatment (e.g., progressive disease (PD), AE)

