- If subsequent treatment was provided within an expanded access programme (EAP)/compassionate use programmes (CUP) or prescribed as clinical practice
- Comorbidities (hepatitis B, gastritis, liver cirrhosis, etc.)
- Concomitant medications including (PPIetc.)
- AEs (leading to dose modification)
- Date & Cause of death

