9.7.1 Main analysis

All patients treated with afatinib will be included in the analysis of the primary outcome, Time on Treatment (TOT) on afatinib. Time on Treatment (TOT) will be evaluated by Kaplan-Meier analysis. Median Time on Treatment (TOT) and two-side 90% CI, and the quartiles will be calculated from the Kaplan-Meier curve. Patients who are lost to follow up without providing the end date of treatment with afatinib will be censored at the time of last known contact.

Overall survival (OS) will be evaluated by Kaplan-Meier analysis. Median overall survival (OS) and two-side 90% CI, and the quartiles will be calculated from the Kaplan-Meier curve. Patients who are lost to follow up (including patient withdrawal) without providing the end date of treatment will be censored at the time of last known contact. Patients who reach the end of study period without providing the end date of treatment will be censored at the end of study.

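### SAP 7.6 censors patients known to have stopped afatinib, or to have died, when the end date lacks more than the day, against its own time-on-treatment definition and Rule 3

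*SAP*

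**What the plan says.** SAP 7.6 defines TOT as "time from the start of afatinib to last dose date of afatinib or death date by any cause, which comes first". Table 7.6:1 then sorts patients into three groups:

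- Rule 1 censors patients lost to follow-up on afatinib without an end date.
- Rule 2 censors patients still on first-line afatinib at the end of the study.
- Rule 3 makes every other situation an event, dated at "Date of last treatment during first line afatinib treatment period".

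Below the table, an incomplete end date is imputed only if month and year are known. For the rest the SAP says "For all other cases, the missing dates will not be imputed and the subject will censored at last known of contact date", and it records a reason that the table does not contain: "censored situation will be missing treatment end date".

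The derivation of last contact begins "For subjects who withdrew from study or became lost to follow-up, the date last known of contact will be based on" and covers no other patients. Rules 1 and 2 limit last contact to the afatinib period; the catch-all does not.

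Protocol 9.7.1 says "Patients who are lost to follow up without providing the end date of treatment with afatinib will be censored" at last known contact. Protocol 9.3 lists "Reason for discontinuation of afatinib treatment" and "Date & Cause of death" among the variables collected, and SAP 7.7.1 uses second-line start dates. SAP section 4 declares no change to the planned analysis.

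**The concern.** Take a patient with a recorded reason for stopping and a recorded second-line start, but only the year of the last afatinib dose. The event has happened; only its date is vague. Under the definition and Rule 3 this patient is an event. Under the catch-all the patient is censored, possibly at a contact long after afatinib ended, because the protocol follows patients to death, loss, withdrawal or December 2023. Two programmers could code the same record differently.

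TOT is the only primary outcome and its median is the main result. Turning known events into censored times pulls in one direction: in expectation it lengthens the median.

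**Working it through.** **1. Classifying the patient above.** Rule 1: not lost, so it does not apply. Rule 2: not on treatment, so it does not apply. Rule 3: event, but without a usable date. Catch-all: censored. Censoring date: not derived, since the patient is neither withdrawn nor lost. A death with an unusable last-dose date meets the same gap. A death with a usable last-dose date does not, because the last dose cannot follow death and Rule 3 then agrees with the definition.

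**2. Design inputs and the plan's own event count.** Protocol 9.5: N = 76, exponential TOT with median 12 months (λ = ln 2/12 = 0.0578 per month), 30% drop-out, 35 events expected. Protocol milestones: accrual A = 19 months (May 2020 to December 2021), then F = 24 months. The time scale of the drop-out is not stated. I read it as 30% of patients leaving before they stop afatinib, which gives η = 0.0273 per month and h = λ + η = 0.0851. Expected stops:

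N × (λ/h) × [1 − (e^(−hF) − e^(−h(F+A)))/(hA)] = 76 × 0.679 × [1 − (0.130 − 0.026)/1.616] = 76 × 0.679 × 0.936 = 48.3.

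The 35 is not reproduced. This point does not rest on it, but step 6 uses a lower count as well.

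**3. Closed form.** Let a share p of stops, at random, be censored instead.

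- Censored at the stop: the hazard becomes (1 − p)λ and the median 12/(1 − p). For p = 2/5/10/20% this is 12.24/12.63/13.33/15.00 months.
- Contact continuing indefinitely: the median is 12 × log2{1/[1 − 0.5/(1 − p)]}, or 12.36/12.94/14.04/16.98. At 5%: 0.5/0.95 = 0.526, 1/0.474 = 2.11, log2 = 1.078, times 12 = 12.94.

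**4. Simulation under the study's follow-up.** Large-sample Kaplan-Meier medians. Assumptions: visits every 28 days (SAP 6.7; the protocol mandates none), median survival of 19 months after the stop, and unusable dates at random among stops.

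| Share of stops with an unusable date | 2% | 5% | 10% | 20% |
|---|---|---|---|---|
| Patients, of about 48 stops | 1 | 2 | 5 | 10 |
| Censored at last visit on afatinib | 12.2 | 12.6 | 13.3 | 15.0 |
| Censored at last contact in all follow-up | 12.4 | 12.9 | 13.9 | 16.6 |

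If deaths on treatment (assumed 10% of stops) stay events, the rows become 12.2/12.6/13.2/14.6 and 12.3/12.8/13.7/16.0.

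**5. Timing.** If the same number of unusable dates falls only on stops after 13 months, the median does not move at 5% or 10%. If it falls only on stops before 12 months, 5% gives about 12.9-13.2 months.

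**6. Single datasets of 76.** With about 48 stops, the median rose in 34-42% of datasets at a 2% rate and in 67-76% at 5%. With drop-out raised to leave about 38 stops, nearer the plan's 35, it rose in about 24-33% and 54-65%. Otherwise it was almost always unchanged; with about 48 stops it fell in 0.1% or fewer.

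**7. Direction.** If the censoring date is on or after the stop, the Kaplan-Meier curve cannot fall at any time, so neither can the median. If it precedes the stop, a small local dip is possible, which explains the rare falls.

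**The case against.** The strongest reply is that the catch-all is the specific rule for a case that Rule 3 cannot handle, since Rule 3 needs a date. It is prespecified, SAP 6.6 points to it, and its label together with the raw-data listings makes the affected patients identifiable. Protocol 9.7.1 also does not say that only lost patients may be censored. This stands in part. A reader might infer that the protocol forbids the rule; it does not, and the SAP goes beyond what the protocol provides. But lacking an exact date does not turn a known stop into an unobserved one, and the table and the text below it still disagree.

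The second reply concerns materiality, and it largely stands. Direct prospective entry, checks at entry, ongoing queries (Protocol 9.6.2) and full verification of critical data (Protocol 9.8) may keep such dates rare. The eCRF is not among the documents, so whether it accepts a year-only date is unknown. The study is descriptive. A reader might infer that the primary result will be materially too long. The documents do not support that: the 10% and 20% columns only show a range, and the random-missingness assumption is one of several possibilities.

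A reader might also see a separate contradiction over deaths. There is none beyond deaths whose last-dose date is unusable.

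**Conclusion.** The conflict is in the current SAP text and exists at any rate of missing dates. For known stops and deaths with an unusable end date, the catch-all contradicts the TOT definition and Rule 3, and the censoring date is undefined for a stopped patient still followed. In expectation the effect on the median is upward or nil.

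Its size is conditional. At 2-5% of stops, at random, it is 0.2 to 0.9 month on a 12-month median. That is small beside the design target in Protocol 9.9.3, an 80% chance that the 90% CI is no wider than 11 months. With no unusable dates there is no effect. Confidence is high on the inconsistency and the direction, and limited on the size. It should be fixed because it is a one-directional, avoidable ambiguity in the primary analysis.

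**What to change.** Reconcile the catch-all with Table 7.6:1:

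1. Code a known stop or death as an event even when the end date is incomplete.
2. Date it within the interval from the last date documented on afatinib to the earliest of second-line start, death or last contact, restricted to the known year if given. Prespecify one rule, such as the midpoint or an interval-censored analysis. Report both bounds as sensitivity analyses, and the number of patients affected.
3. For a death without a usable last-dose date, use the death date only if nothing shows an earlier stop.
4. Keep censoring, at last contact during the afatinib period, for patients lost or withdrawn with no evidence of stopping.

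The cost is SAP wording and minor programming on fields already collected. The downside is that a few event dates are known only within an interval. With the midpoint (death date for deaths) and second-line start assumed 0.25-2 months after the stop, the median at 2/5/10/20% is 12.00/12.01/12.02/12.04 months. If 30% have no second-line start to bound the interval, a small upward bias remains: 12.04/12.11/12.22/12.43, or 12.01/12.03/12.07/12.13 when the year is known.
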